### **10.6 Infection Monitoring**

Monitoring for infection will be performed at screening and for the duration of study therapy per institutional practice and will assess for the following at a minimum: Monitoring for cytomegalovirus, Epstein-Barr virus, human T-cell lymphotropic virus 1 and 2, and Toxoplasmosis IgM and IgG will be performed at screening. Prior test results obtained as part of standard of care before allo-HCT may be used for purposes of eligibility and tests do not need to be repeated. Routine Infection monitoring should occur during the study as per institutional practice and include at a minimum PCR testing on plasma for CMV and EBV and monitoring for fungal infections (i.e. Aspergillus).

Additional monitoring should be performed during treatment if there is clinical suspicion of an infection; outcomes should be reported as adverse events as appropriate.

### **10.7 Graft Failure and Chimerism Monitoring**

Participants will be monitored for evidence of graft failure during study treatment and post-treatment follow-up. The monitoring of graft failure will be primarily based on the monitoring of blood counts and supported by chimerism studies. Secondary graft failure will be defined as a decrease of ANC  $< 0.5 \times 10^9/L$  on at least 3 subsequent laboratory assessments without another potential etiology or  $< 95\%$  recipient cells any time after engraftment with no signs of relapse.

Donor chimerism after an allo-HCT involves identifying the genetic profiles of the recipient and of the donor pre-transplant and then evaluating the ratio of donor to recipient cells in the recipient's blood or bone marrow. Chimerism testing using peripheral blood or bone marrow will be performed at the treating investigator's discretion according to local institutional practice.

If a participant experiences graft failure, any action taken to manage the graft including rapid taper of immunosuppression, administration of nonscheduled DLI, stem cell boost, or other intervention(s) should be documented in the patient's research chart.

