### 5.1 Inclusion Criteria

**Yes/No (Response of "no" = patient ineligible)**

- 5.1.1 \_\_\_\_\_ Male or female subject aged  $\geq 18$  years.
- 5.1.2 \_\_\_\_\_ Active, clinically diagnosed, moderate or severe chronic GVHD as defined by the NIH Consensus Development Project Criteria (See Appendix 2).
- 5.1.3 \_\_\_\_\_ History of an allogeneic hematopoietic cell transplant with any conditioning regimen, donor, or graft source.
- 5.1.4 \_\_\_\_\_ Need for systemic treatment for chronic GVHD as assessed by the treating investigator.
- 5.1.5 \_\_\_\_\_ No previous systemic treatment for chronic GVHD.
- Note: Participants may be receiving immunosuppressants for the prophylaxis or treatment of acute GVHD, but these medications must have been stable for at least 2 weeks prior to the initiation of study therapy. Prednisone dose (or its equivalent) should be at doses of  $\leq 0.25$  mg/kg/d for at least 2 weeks prior to the initiation of study therapy.
- Topical or inhaled treatments for chronic GVHD are allowed. Any prior ECP treatments for the management of acute GVHD must have occurred  $> 4$  weeks prior to the initiation of itacitinib treatment.
- 5.1.6 \_\_\_\_\_ Able to swallow and retain oral medication.
- 5.1.7 \_\_\_\_\_ Life expectancy  $> 24$  weeks.
- 5.1.8 \_\_\_\_\_ Karnofsky performance status  $\geq 60$
- 5.1.9 \_\_\_\_\_ Evidence of myeloid and platelet engraftment:
- Absolute neutrophil count  $\geq 1000/\text{mcL}$
  - Platelet count  $\geq 25,000/\text{mcL}$

Note: Use of growth factors and transfusion support is allowed during the study; however, growth factors and transfusion support to reach a minimum ANC or

platelet count for inclusion are not allowed within the 7 days before the screening laboratory assessment.

**5.1.10** \_\_\_\_\_ Adequate organ function as defined as:

- **Hepatic:**
  - Total bilirubin  $\leq 2$  mg/dL
  - AST(SGOT)/ALT(SGPT)  $\leq 2.5 \times$  institutional ULN (unless of non-hepatic origin). AST/ALT  $\leq 5 \times$  ULN is acceptable if associated with chronic GVHD.
- **Renal:**
  - eGFR  $\geq 30$  mL/min/1.73 m^2 as calculated using the Modification of Diet in Renal Disease formula or by the Cockcroft-Gault formula:
    - Males:  $\frac{(140 - \text{age}) \times \text{weight}[\text{kg}]}{\text{serum creatinine} \left[ \frac{\text{mg}}{\text{dL}} \right] \times 72}$

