## 5.2 Exclusion Criteria

### Yes/No (Response of “yes” = patient ineligible)

- 5.2.1 \_\_\_\_\_ Subjects with score 3 lung GVHD or biopsy-proven bronchiolitis obliterans.
- 5.2.2 \_\_\_\_\_ Participants have uncontrolled manifestations of acute GVHD.
- 5.2.3 \_\_\_\_\_ Treatment with any investigational medication within  $\leq 30$  days or 5 half-lives, whichever is longer, before the first dose of study drug.
- 5.2.4 \_\_\_\_\_ Patients who have received any previous systemic treatment for chronic GVHD, including corticosteroids, prior to Cycle 1, Day 1.
- Note: Prior and concomitant use of Calcineurin-Inhibitors (CNIs) for prevention and treatment of acute GVHD, as well as topical/inhaled steroids, is acceptable.
- 5.2.5 \_\_\_\_\_ Received prior JAK inhibitor therapy for any indication  $\leq 4$  weeks prior to Cycle 1 Day 1.
- 5.2.6 \_\_\_\_\_ Patients with relapsed or progressive malignant disease or any post-transplant lymphoproliferative disease.
- 5.2.7 \_\_\_\_\_ Chronic GVHD occurring after a non-scheduled donor lymphocyte infusion (DLI) administered for pre-emptive treatment of malignancy recurrence. Participants who have received a scheduled DLI as part of their transplant procedure and not for management of malignancy relapse are eligible.
- 5.2.8 \_\_\_\_\_ Inability to swallow food or any condition of the upper gastrointestinal tract that precludes the administration of oral medications.
- 5.2.9 \_\_\_\_\_ Any contraindication for extracorporeal photopheresis (ECP) per the treating investigator’s discretion.
- 5.2.10 \_\_\_\_\_ Subject has a concurrent illness which in the opinion of the investigator may interfere with the treatment and evaluation of the subject.
- 5.2.11 \_\_\_\_\_ Pregnant or currently breast-feeding.

Note: INCB039110 is a JAK1 inhibitor with the potential for serious or life-threatening birth defects or abortifacient effects. Because there is an unknown but potential risk for adverse events in nursing infants secondary to treatment of

the mother with INCB039110, breastfeeding should be discontinued if the mother is treated with INCB039110. These potential risks may also apply to other agents used in this study.

- 5.2.12** \_\_\_\_\_ Vaccinated with live, attenuated vaccines within 4 weeks of the first dose of study drug and while on trial.

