 Monitoring for infection will be performed at screening and for the duration of study therapy per institutional practice. Testing for cytomegalovirus and Epstein-Barr virus will be performed at screening. Prior test results obtained as part of standard of care before allo-HCT may be used for purposes of eligibility and tests do not need to be repeated. Routine infection monitoring should occur during the study as per institutional practice and include at a minimum PCR

testing on plasma for CMV and EBV and monitoring for fungal infections (i.e. Aspergillus). Additional monitoring should be performed during treatment if there is clinical suspicion of an infection.

 Screening assessment may be used if completed within 7 days prior to C1D1.

 Graft failure/chimerism should be performed on whole blood and should include: Chimerism, Post-Transplant and Chimerism, Post-Cell Sort, T cells.

 Participants will be closely monitored for any evidence of underlying disease relapse or recurrence during study therapy. These evaluations will be conducted in accordance with local institutional practices.

 To be completed prior to the physical exam at C1D1, C2D1, C3D1, C6D1, C8D1, C10D1, and EOT or PD visit.

 ECP will be given at a frequency of twice weekly for 8 weeks followed by a standard taper schedule as per study protocol. Refer to Table 4 for taper schedule.

 All patients will undergo 5 to 10 days of itacitinib monotherapy. The first ECP treatment will be considered C1D1. On days that the patient is being seen in clinic, itacitinib dosing does not need to be held prior to routine blood draws or for correlative studies.

 Patients may be on immune suppression at the time of study enrollment. On days that the patient is being seen in clinic, immunosuppressives should be held until after the blood draws if trying to achieve a therapeutic level. See Section 6.1.3.

 Correlative studies are only required during dose expansion. On days of drug administration, correlative blood samples should be drawn without regard to itacitinib dosing or ECP therapy. Patients should take itacitinib at their usual time. Blood will be drawn at screening, C1D1, the time of response, C7D1, and at EOT or progression, whichever occurs first.

 Only to be drawn from the first nine patients enrolled in Part 2, Dose Expansion.

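### The chimerism limb of the secondary graft failure definition in Section 10.7 is inverted: full donor chimerism meets it, and near-complete loss of donor cells does not

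*Combined protocol and SAP*

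**What the plan says.** Section 10.7 commits the trial to watching for graft failure during treatment and follow-up. It describes that monitoring as "primarily based on the monitoring of blood counts and supported by chimerism studies". The definition of secondary graft failure has two limbs joined by or:

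- **Neutrophil limb:** ANC < 0.5 × 10⁹/L "on at least 3 subsequent laboratory assessments without another potential etiology or".
- **Chimerism limb:** < 95% "recipient cells any time after engraftment with no signs of relapse".

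The same section explains chimerism as "evaluating the ratio of donor to recipient cells in the recipient's blood or bone marrow". If graft failure occurs, whatever is done about it is to be written in the research chart.

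On who is tested and how, the plan speaks twice. Section 10.7 says: "Chimerism testing using peripheral blood or bone marrow will be performed at the treating investigator's discretion according to local institutional practice". Table 7 has a chimerism row in the schedule, and its footnote 22 says: "Graft failure/chimerism should be performed on whole blood and should include: Chimerism, Post-Transplant and Chimerism, Post-Cell Sort, T cells".

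**The concern.** A graft failure criterion should pick out patients who are losing donor cells. As worded, the chimerism limb picks out patients who still have them. Because the limbs are joined by or, the chimerism limb can classify a patient on its own, whatever the blood counts show.

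At stake is a safety definition that sites are expected to apply throughout treatment and follow-up, for a drug whose animal studies showed reduced marrow cellularity (Section 3.1.3). Followed literally, it records successful engraftment as failure. It also overlooks a graft loss that shows on chimerism while neutrophils hold up. If each site silently corrects it, sites may correct it differently.

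The testing instructions add to this. One place schedules a defined pair of blood tests. The other leaves testing to judgement and allows marrow as well. The percentage itself is tied to no specimen.

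**Working it through.** There is no sample size, power or error rate to reproduce here. The check is to apply the written rule across the range of chimerism.

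**Inputs**

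- Chimerism limb: recipient % < 95, after engraftment, no signs of relapse (Section 10.7).
- Chimerism compares donor with recipient cells (Section 10.7), so recipient % = 100 − donor %.
- Entry requires "Evidence of myeloid and platelet engraftment" (Section 5.1.9), judged by neutrophil and platelet counts, with no chimerism threshold.
- Entry excludes "Patients with relapsed or progressive malignant disease or any post-transplant lymphoproliferative disease" (Section 5.2.6). For patients transplanted for malignancy, the no-relapse condition is therefore normally met at the start.

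**Step 1. Rewrite the limb.** Recipient % < 95 means 100 − donor % < 95, which gives donor % > 5.

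**Step 2. Apply it to a patient without relapse, beside the two simplest repairs.** Repair A changes the sign (> 95% recipient, that is donor < 5%). Repair B changes the cell source (< 95% donor, that is recipient > 5%).

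| Recipient % | Donor % | As written | Repair A | Repair B |
|---|---|---|---|---|
| 0 | 100 | meets | does not | does not |
| 5 | 95 | meets | does not | does not |
| 50 | 50 | meets | does not | meets |
| 94 | 6 | meets | does not | meets |
| 95 | 5 | does not | does not | meets |
| 100 | 0 | does not | meets | meets |

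The written rule is wrong at both ends: it flags full donor chimerism and passes complete donor loss. The repairs agree at the ends but give opposite answers for mixed chimerism, roughly 5% to 95% recipient.

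**Step 3. Look for a correction elsewhere.** Table 7, its footnote 22 and Table 8 list the chimerism tests without a cut-off. Nothing overrides Section 10.7, and nothing shows which repair was meant.

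**Step 4. Trace where the definition is used.** Graft failure does not appear in the objectives and endpoints (Section 1), including failure-free survival. It is also absent from the dose-limiting toxicity table (Table 3), the off-treatment criteria (Section 6.7.1), the stopping rules (Section 11.3) and the planned analyses (Section 12.4).

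**Step 5. Compare the testing instructions.** Section 10.7: blood or marrow, at discretion. Table 7 and footnote 22: a scheduled test on whole blood, including sorted T cells. Both cannot govern. This step relies only on the row being scheduled, not on which visits are marked.

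**The case against.** The best defence is that little depends on this definition. Blood counts are the stated primary basis, the neutrophil limb is correctly worded, and hematology is scheduled at the treatment visits, so graft loss with sustained low neutrophils is still captured. A clinician would see at once that a full-donor result is not graft failure. All of this stands, and it limits the consequences. It does not make the chimerism limb usable, because that limb can classify a patient by itself and the obvious corrections disagree.

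A misread sign in the text cannot be wholly excluded. However, the ANC inequality in the same sentence reads as expected, and the sponsor can settle the point from its source file.

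A reader might infer several stronger conclusions that the documents do not support:

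- **That the trial will report a graft failure rate near 100%.** No section plans to compute such a rate.
- **That false labels will lead to faster withdrawal of immunosuppression or unscheduled donor lymphocytes and so disturb the 24-week response.** Section 10.7 asks only that any action taken be documented. It directs none, so this chain requires an investigator to act against a reassuring result.
- **That every graft loss is missed.** The gap is graft loss seen on chimerism without the sustained low neutrophil count that the other limb requires.
- **That only patients who have lost the graft escape the definition.** Such patients can still qualify through neutrophils, and patients with signs of relapse also fall outside the chimerism limb.

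**Conclusion.** The point holds for the chimerism limb. As written, that limb equals more than 5% donor cells. It labels a relapse-free patient with full donor chimerism as a secondary graft failure and leaves a patient with 95% to 100% recipient cells and preserved neutrophils outside both limbs. This follows from the plain text and needs no outside figure.

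How many enrolled patients would be mislabelled depends on their chimerism, which the documents do not give. If all have more than 5% donor cells, all who are relapse-free would meet the limb when tested. That is plausible given required engraftment and active chronic GVHD, but it remains an assumption because entry sets no chimerism threshold.

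The severity is moderate. Sample size, error rates, the stage 1 decision and the toxicity boundary are untouched. What suffers is the safety monitoring and recording of graft failure. The conflict over discretionary versus scheduled testing is a lesser, related defect.

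**What to change.** 1. Restate the chimerism limb in Section 10.7 so that full donor chimerism cannot meet it. The sponsor confirms whether the inequality or the cell source is wrong and whether the percentage stands. The documents do not settle this, and the choice decides how mixed chimerism is classified.
2. State which specimen the percentage applies to: whole blood, sorted T cells or marrow.
3. Reconcile the discretion sentence in Section 10.7 with the chimerism row and footnote 22 of Table 7, so that a site can tell whether the test is required and on what sample.

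The cost is one corrected definition and one aligned sentence in an amendment. Table 7 already schedules the testing, and no design calculation changes.

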### **10.8 Disease Malignancy/Relapse**

Hematologic Disease Relapse Monitoring Participants will be closely monitored for any evidence of underlying disease relapse or recurrence at each visit during treatment, EOT, and follow-up periods of the study. These evaluations will be conducted in accordance with local institutional practices. Details on malignant and nonmalignant hematologic disease relapse and subsequent management should be collected on the appropriate eCRF.

## **10.9 Chronic GVHD Assessment**

GVHD response will be assessed according to the NIH Consensus Development Project Criteria. The chronic GVHD activity assessment forms as provided by clinicians and patients will also be collected (Appendix 5 and 6). These assessments will occur after two, four, and eight weeks of treatment and then monthly thereafter. The primary efficacy endpoint will be evaluated at 24 weeks. Patients with responding disease may continue therapy for up to 12 months.

## **10.10 Pulmonary Function Test**

Pulmonary function tests (PFTs) including spirometry with forced expiratory volume in 1 second (FEV1) and assessment of Diffusing Capacity for Carbon Monoxide (DLCO) is required at the Screening Visit. Thereafter, spirometry only is required at protocol-specific time-points as defined in the Schedule of Events. PFTs may be conducted  $\leq 7$  prior to the following day one visit to allow for timely review of results.

## **10.11 AM-PAC**

The Activity Measure for Post Acute Care (AM-PAC) Basic Mobility Outpatient Routine Short Form will be completed at the time-points specified on the Schedule of Events. See Appendix 7.

## **10.12 2-minute Walk Test**

A 2-minute walk test will be conducted at the time-points specified on the Schedule of Events. Patients will be instructed to walk without assistance for 2 minutes and the distance traveled in feet will be recorded in the eCRF. Patients should be instructed to walk at the fastest speed possible for the entire two minutes, but it is acceptable to slow down or stop as necessary. A walk test should not be conducted in the event that a patient is unable to walk without assistance and this should be clearly documented in the patient's chart.

# **11 CRITERIA FOR EVALUATION AND ENDPOINT**

## **11.1 Safety**

Routine safety and tolerability will be evaluated from the results of reported signs and symptoms, scheduled physical examinations, vital sign measurements, and clinical laboratory test results. More frequent safety evaluations may be performed if clinically indicated or at the discretion of the investigator.

## **11.2 Efficacy**

GVHD response will be determined by the NIH Consensus Development Project Criteria (see Appendix 4). At each post-baseline assessment, each organ must be assessed using the same criteria as for baseline, and response should be determined by comparing the current organ assessment with the baseline organ assessment on Day 1. A summary of organ-specific response assessment criteria as per NIH consensus guideline is provided below.

**Table 9: Organ Assessments**

Organ	Evaluation	Criteria
Skin	NIH Skin Score, considering %BSA involvement and sclerotic features	Change of Skin score
Eyes	NIH Eye score	Change of Eye score
Mouth	NIH Modified OMRS (sum of scores for erythema, lichenoid, and ulcers)	Change of OMRS
Esophagus	NIH Esophagus score	Change in Esophagus score
Upper GI	NIH Upper GI score	Change in Upper GI score
Lower GI	NIH Lower GI score	Change of Lower GI score
Liver	Lab results for ALT, ALP, and total bilirubin	Change in values of lab results
Lungs	NIH Lung score and %FEV1	Change in %FEV1
Joints and fascia	NIH Joint and Fascia score and P-ROM scores	Change of Joint and Fascia score and P-ROM scores

**Table 10: Post-baseline Response Evaluations**

Organ		Organ-Specific Response			
Skin	CR/not involved	PR in at least 1 organ with baseline involvement AND no progression in any other organ (i.e., CR, PR, unchanged, or no involvement)	PR or CR in 1 or more organ(s) with baseline involvement AND progression in 1 or more organs (incl. new occurrence in an organ with no baseline involvement)	Progression in 1 or more organ(s) with baseline involvement OR new occurrence in an organ with no baseline involvement AND no CR or PR in any other organ	Organ-specific response 'unchanged' for all organs (incl. no involvement)
Eyes					
Mouth					
Esophagus					
Upper GI					
Lower GI					
Liver					
Lungs					
Joints and Fascia					
Overall Response	CR	PR	MR	PD	Unchanged

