**Date**

**Appendix 4: NIH Criteria for Response Assessment of Chronic GVHD**

Organ	Complete Response	Partial Response	Progression
Skin	NIH Skin Score 0 after previous involvement	Decrease in NIH Skin Score by 1 or more points	Increase in NIH Skin Score by 1 or more points, except 0 to 1
Eyes	NIH Eye Score 0 after previous involvement	Decrease in NIH Eye Score by 1 or more points	Increase in NIH Eye Score by 1 or more points, except 0 to 1
Mouth	NIH Modified OMRS 0 after previous involvement	Decrease in NIH Modified OMRS of 2 or more points	Increase in NIH Modified OMRS of 2 or more points
Esophagus	NIH Esophagus Score 0 after previous involvement	Decrease in NIH Esophagus Score by 1 or more points	Increase in NIH Esophagus Score by 1 or more points, except 0 or 1
Upper GI	NIH Upper GI Score 0 after previous involvement	Decrease in NIH Upper GI Score by 1 or more points	Increase in NIH Upper GI Score by 1 or more points, except 0 or 1
Lower GI	NIH Lower GI Score 0 after previous involvement	Decrease in NIH Lower GI Score by 1 or more points	Increase in NIH Lower GI Score by 1 or more points, except from 0 to 1
Liver	Normal ALT, alkaline phosphatase, and Total bilirubin after previous elevation of 1 or more	Decrease by 50%	Increase by 2 x ULN
Lungs	
 
• Normal % FEV1 after previous involvement
 
• If PFTs not available, NIH Lung Symptom Score 0 and P-ROM score 25 after previous involvement by at least 1 measure
 
	
 
• Increase by 10% predicted absolute value of %FEV1
 
• If PFTs not available, decrease in NIH Lung Symptom Score by 1 or more points
 
	
 
• Decrease by 10% predicted absolute value of % FEV1
 
• If PFTs not available, increase in NIH Lung Symptom Score by 1 or more points, except 0 to 1
 

Joints and facia	Both NIG Joint and Fascia Score 0 and P-ROM Score 25 after previous involvement by at least 1 measure	Decrease in NIH Joint and Fascia Score by 1 or more points or increase in P-ROM score by 1 point of any site	Increase in NIH Joint and Fascia Score by 1 or more points by 1 point for any site
Global	Clinician overall severity score 0	Clinician overall severity score decreases by 1 or more points on a 0-10 scale	Clinician overall severity score increases by 2 or more points on a 0-10 scale

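### Table 10 scores any new organ involvement as progression, although Appendix 4 exempts low-grade new involvement in several organs; separately, 4.1 and 9.3 disagree on whether a progressing patient stays on therapy

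*Combined protocol and SAP*

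**What the plan says.** Section 11.2 names the criterion: "GVHD response will be determined by the NIH Consensus Development Project Criteria (see Appendix 4"). It introduces the material that follows as a summary: "A summary of organ-specific response assessment criteria as per NIH consensus guideline is provided below".

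Table 10 then turns organ results into an overall response. Its PR column requires "PR in at least 1 organ with baseline involvement AND no progression in any other organ (i.e., CR, PR, unchanged, or no involvement"). Its MR column pairs a response in one organ with "progression in 1 or more organs (incl. new occurrence in an organ with no baseline involvement"). Its PD column adds a free-standing alternative: "OR new occurrence in an organ with no baseline involvement AND no CR or PR in any other organ". Neither MR nor PD counts towards ORR.

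Appendix 4 sets organ thresholds for progression. For skin: "Increase in NIH Skin Score by 1 or more points, except 0 to 1". For eyes: "Increase in NIH Eye Score by 1 or more points, except 0 to 1". For mouth: "Increase in NIH Modified OMRS of 2 or more points". Lower GI has the 0-to-1 exception, as does the lung symptom score when PFTs are unavailable. The esophagus and upper GI rows print the exception as 0 or 1.

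The Study Summary, 12.1 and 12.4.1 (Part 2) all score progression before week 24 as non-response. Section 9.3 discontinues study therapy on progression. Section 4.1 allows prednisone up to 0.25 mg/kg/d during study treatment for GVHD that is progressing or responding poorly, and says that adding it is not a primary-endpoint failure.

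**The concern.** The primary endpoint depends on what counts as progression, and the plan gives two answers for the same finding. Appendix 4 has no rule that combines organs (its global row is a separate clinician rating), so a scorer has to use Table 10. Read literally, Table 10 overrides the thresholds that 11.2 says apply. Nothing states which prevails.

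The trial is open-label and single-arm, with cut-offs of 7 v 8 responses in 16 and 23 v 24 in 46. A choice between the tables made once results are visible could decide either look. The difference also acts before week 24, because 10.9 starts GVHD assessments at week 2. A new score of 1 at an early visit could then end a patient's therapy as well as fix the endpoint.

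Sections 4.1 and 9.3 raise a second question about patient management: one keeps a progressing patient on treatment with low-dose prednisone, the other takes the patient off.

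**Working it through.** **1. The two rules side by side, for an organ uninvolved at baseline.**

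| Organ | Appendix 4 | Table 10, MR and PD columns |
|---|---|---|
| Skin, eyes, lower GI | 0 to 1 is not progression | progression |
| Esophagus, upper GI | evidently the same (misprinted) | progression |
| Lung symptom score, PFTs unavailable | 0 to 1 is not progression | progression |
| Mouth (OMRS) | needs a rise of 2 or more, so 0 to 1 is not progression | progression |
| Joints and fascia | a 1-point rise is progression | progression (agrees) |
| Liver, %FEV1 | own numerical thresholds | no threshold stated |

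**2. One patient, two results.**
- At C7D1, mouth PR and skin 0 to 1. With Appendix 4 thresholds no organ has progressed, so the patient is PR. With Table 10's new-occurrence wording the patient is MR, a non-responder.
- At week 2, skin 0 to 1 and no organ yet responding. With Appendix 4 this is not progression. With Table 10 it is PD, so 12.4.1 gives non-response and 9.3 stops therapy.

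**3. The plan's own figures.** Inputs from 12.1 and 12.4.1: 16 patients in stage 1, continue with 8 or more responses; 30 more patients; reject the null with 24 or more of 46.

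P(success at p) = sum over x = 8 to 16 of P[Bin(16, p) = x] × P[Bin(30, p) ≥ 24 − x].

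At p = 0.40 this gives 0.0486, and at p = 0.60 it gives 0.8006. Both stated figures reproduce.

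**4. Illustrative cost of Table 10 as printed.** Assume that true ORR by Appendix 4 is 60% and that Table 10 moves a share f of those responders to non-response. The rate under test becomes 0.60 × (1 − f).

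| f (assumed) | Patients re-scored per 46 (27.6 × f) | Effective rate | P(stop at stage 1) | Power |
|---|---|---|---|---|
| 0 | 0 | 0.600 | 0.142 | 0.801 |
| 2% | 0.55 | 0.588 | 0.166 | 0.760 |
| 5% | 1.38 | 0.570 | 0.206 | 0.690 |
| 10% | 2.76 | 0.540 | 0.283 | 0.554 |

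Here 27.6 = 46 × 0.60. If a treatment with a 40% Appendix 4 rate is re-scored by the same shares, the chance of rejection falls from 0.0486 to 0.039, 0.027 and 0.014. So the printed Table 10 errs towards rejecting the treatment.

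**5. Sections 4.1 and 9.3.** For a patient whose GVHD progresses and who receives prednisone at or below 0.25 mg/kg/d, 4.1 describes the drug as given while on study treatment. Section 9.3 discontinues that treatment, with no exception for such a patient. The two cannot both be followed.

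**The case against.** The best defence of Table 10 is that it only rolls up organ results. Section 11.2 names Appendix 4 as the criterion and calls the rest a summary, organ-level progression is defined only in Appendix 4, and in the MR column new occurrence is a parenthesis attached to progression. On that reading the example patient fits the PR column. This supports Appendix 4 as the intended rule. It does not remove the conflict, because the PD column lists new occurrence as an alternative in its own right, and the MR parenthesis includes it without a threshold.

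A second objection is that the size is unknown. That stands: the documents give no share of patients with new score-1 involvement. The chance of finishing one response short of a cut-off (0.084 + 0.028 = 0.112 at a true 60%) would apply to any one-patient scoring question in this design, so it does not measure this defect.

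Several stronger readings are tempting:
- A reader might infer that 9.3 contradicts 12.4.1. It does not: stopping therapy at progression agrees with scoring progression as non-response. The conflict of 9.3 is with 4.1.
- A reader might infer that 4.1 turns a progressing patient into a possible responder. Its words exempt the addition of prednisone, not the progression, and the non-response rule is stated three times without exception. Section 1.1.2 does not mention interim progression, but silence is not contradiction.
- A reader might infer that the calcineurin-inhibitor or sirolimus increase in 6.6.4 is the only permitted change not tied to the primary endpoint. Section 6.7.1 has a similar provision for reinstating a tapered drug.
- A reader might ask for a sensitivity ORR on steroid use. Week-24 ORR stratified by concurrent prednisone and cumulative prednisone dose are already planned. Concurrent use is not the same as any use, but the overlap is large.

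**Conclusion.** The point holds in two parts. First, Table 10 and Appendix 4 give different primary-endpoint results for a low-grade new finding in skin, eyes, lower GI, mouth, the lung symptom score without PFTs and, once the misprint is read as intended, esophagus and upper GI. A reader might extend this to all low-grade new involvement, but joints and fascia have no exemption, and liver and %FEV1 follow their own thresholds.

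If Appendix 4 is the intended criterion, the printed Table 10 loses responders. The loss of power from 0.80 to between 0.76 and 0.55 rests on an assumed 2% to 10% of responders re-scored, and on a true 60% ORR by Appendix 4. Sample size, type I error and power as stated are correct and are not in dispute.

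Second, 4.1 and 9.3 conflict on whether a patient given low-dose prednisone for progressing GVHD continues study therapy. This concerns conduct of treatment. On the endpoint, 12.4.1 already governs, and one clarifying sentence is enough. The point should be fixed, and is not fatal to the design.

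**What to change.** (a) In the MR and PD columns of Table 10, state that a new occurrence is progression only if it meets the Appendix 4 threshold for that organ. Correct the esophagus and upper GI rows of Appendix 4 so that the exception reads from 0 to 1.

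(b) In 9.3, state whether a patient given prednisone under 4.1 for progressing GVHD stays on study therapy. In 4.1, add one sentence saying that the exemption covers the prednisone and not the progression, which remains non-response under 12.4.1.

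Make both changes before the stage 1 look, so that the choice of rule cannot be linked to the results. The cost is wording and an amendment submitted for IRB approval (16.8). No new data, visits or patients are needed, and the design figures do not change. The downside is that ORR may come out slightly higher than under Table 10 as printed.
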